3. Cirrhosis or any prior liver decompensation event (i.e., ascites, spontaneous bacterial peritonitis, hepatic encephalopathy, esophageal varices, and/or hepatorenal syndrome), defined by review of medical record (including clinical notes, prior liver imaging, procedures and prior liver biopsies where available), and by confirmation from treating medical provider.
4. Severe cardiovascular disease (i.e. myocardial infarction within the last year, left ventricular ejection fraction of less than 40% or active angina), defined by medical record review or by patient self-report
5. Severe renal disease (defined as eGFR less than 30)
6. Pregnancy or desire to become pregnant or breastfeeding.
7. Contraindications to aspirin use, including aspirin intolerance, prior peptic ulcer disease, prior GI or non-GI bleeding
8. Thrombocytopenia
9. Aspirin use within the preceding 3 months
10. Current use of other antithrombotics, anticoagulants, or antiplatelet agents (not including non-aspirin nonsteroidal anti-inflammatory drugs, NSAIDs)
11. Routine MRI exclusion criteria (i.e. metal implants, etc.)
12. Bariatric surgery within the past 2 years
13. Active cancer (i.e. currently undergoing treatment), except for non-melanoma skin cancer.

B. Recruitment:

We will use the following potential techniques for recruitment:

1. Advertisements in newspapers
2. MGH and BWH's "Research Studies Seeking Volunteers" email
3. RSVP for health emailing
4. Internet posting (Craig's List, Facebook)
5. Mass mailings, based on demographic and geographic area
6. Advertise in local newspapers
7. Postering throughout the Boston metropolitan area, with close attention to recruiting minorities
8. Letters to patients from Massachusetts General Hospital, Brigham and Women's Hospital, North Shore Medical Center, Salem Hospital and Faulkner Hospital ("Partners Healthcare System") who have been diagnosed with obesity, fatty liver disease and/or related conditions, based on Partners Healthcare System-approved search of billing records "RPDR" search. Potential subjects will be contacted after signed permission from a provider OR contacted directly if the potential subject has previously signed up for this feature.
9. Recruitment through the MGH Fatty Liver Clinic, The Gastrointestinal Surgery Clinic at MGH and other clinics in which current study staff provide care.
10. Recruitment through the MGH NAFLD Tissue Repository Studies (IRB #: 2009P002081 and IRB #: 2009P002098)

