This visit will be performed during a +/- 2-week interval around the planned date, to accommodate potential scheduling conflicts. A physical examination and measurements of body weight and waist-to-hip ratio will be completed. Study subjects will be assessed for interim medical history, and any side effects to study drug. We will measure a hematocrit.

3. Twice monthly telephone calls or voicemail messages (+/- 1 week):

The trained clinical research coordinator, working directly with the PI, will conduct twice-monthly check-in telephone calls to enrolled subjects on the months when the subject does not have a study visit (i.e. at month 2, month 4 and month 5), using a Partners IRB-approved telephone script. The purpose of these calls will be to ask about medication compliance and to inquire about any concerns or side effects related to the study drug. All subjects will be reminded during this call or voicemail message that the PI ([name]) will be available by pager at all times during the study to answer any questions or concerns that arise.

4. Early Termination Visit:

Subjects who discontinue the study early due to an adverse event, toxicity, or personal reasons will be asked to complete an Early Termination visit. This visit will include all assessments that are performed at the final 6-month visit described above. Participants must have been on the study medication for at least 11 weeks in order to be eligible for completing an Early Termination visit.

5. Remote Visits: Subjects who do not live locally will have the option to perform the 3-month follow-up visit remotely. This will be performed with remote labs (via Quest Diagnostics Locations) and medical history via phone call with a study staff member. For these remote visits, the study staff member will speak to the subject over the phone to review the medical history. If during a phone-medical history, the study staff member believes the subject may be experiencing side-effects related to the study medication, the PI will be notified and the subject will be informed that they need to come to MGH for a physical exam. For these remote visits, the study team will FedEx study medication to the subject in a manner approved by the research pharmacy as needed for resupply. The subject would bring back unused study medication and empty vials to the study team at the next in person visit to maintain standard study drug accountability logs.

B. DRUGS

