Aspirin: Aspirin 81mg tablets (generic; purchased directly by the MGH Research Pharmacy and made into blinded aspirin capsules that are identical to placebo capsules).

Placebo: Blinded placebo capsules that are identical to the aspirin capsules will be prepared by the MGH Research Pharmacy (purchased directly by the MGH Research Pharmacy).

Rationale for dose: Dosing is based on U.S. Preventive Services Task Force prior recommendations for consideration for primary CV and colorectal cancer (CRC) prevention⁹. Use of 81mg/day is also consistent with another active RCT of aspirin for CRC prevention (NCT02394769)¹⁰. Aspirin is not contraindicated in NAFLD. Nevertheless, bleeding with aspirin is dose-dependent¹¹, so the choice to use low-dose aspirin (81mg per day daily dose) will optimally balance safety and efficacy.

Rationale for duration: 6 months is recommended for early-phase NAFLD clinical trials by the AASLD⁸, is widely used¹²⁻¹⁴, and is sufficient to reveal changes in fat¹⁵⁻²¹, thus this trial duration appropriately balances efficacy and compliance.

The risks of low-dose (81mg) aspirin treatment include aspirin allergy or intolerance, with or without associated bronchospasm, gastrointestinal (GI) upset, risk for peptic ulcer disease, and bleeding, including GI bleeding, intracranial bleeding and bleeding from other sites^{11, 22-24}. We have taken several steps to minimize these potential risks. First, we have selected a low daily aspirin dose (81mg per day), which minimizes potential bleeding or ulcer-related risks, compared to higher doses. Second, we will exclude any subject with a personal history of aspirin intolerance, and anyone with a personal history indicating an increased risk for bleeding, including: personal history of bleeding or stroke, and/or history of coagulopathy and/or thrombocytopenia, and/or any subject with current use of any other anti-coagulant or antithrombotic medications. Third, we will conduct a 3-month visit with assessment of safety labs (hematocrit), as well as an interval history and physical examination to assess for any interval bleeding. Finally, we will conduct twice-monthly telephone check-ins that will further enhance safety by giving subjects additional opportunities to further discuss any issues or concerns. Importantly, we will ensure that all subjects are aware of and understand these risks, through our informed-consent process.

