MRI and MR spectroscopy will be performed twice during this prospective study (baseline and final 6-month visit) using FDA-approved devices and pulse sequences. A standard MRI questionnaire will be administered to all potential study subjects, and no study subject with a contraindication to MR testing will be admitted to the study. There are no known foreseeable risks associated with exposure to MRI, provided patients are appropriately screened and there are no metallic implants (i.e. vascular clamps or pacemakers). All potential subjects will be carefully screened for the presence of such implants or any other contraindication to MRI, prior to each exam. No study subject with a contraindication to MR testing will be admitted to the study. Some subjects report some claustrophobia during MRI scans. If a patient expresses any discomfort whatsoever during the scan, the procedure will be aborted and not repeated without his/her full consent.

Risks of Stool Collection:

Stool will be collected using a stool collection kit that contains some special preservatives to make sure they are stable over time. If skin comes into contact with these preservatives, they could irritate the skin. The preservative can simply be washed off with soap and water.

Risks of Genetic Testing

Genetic information that results from this study does not have medical or treatment importance at this time. However, there is a risk that information about taking part in a genetic study may influence insurance companies and/or employers regarding a subject's health. To safeguard the privacy of our subjects, genetic information obtained in this study will not be shared or made available to be placed in the medical record. Taking part in a genetic study may also have a negative impact on family or other personal relationships.

We will in no way discourage use of any medications that are clinically indicated for the subject. Subjects will be discontinued from the study if they start a medication that is known to affect liver fat, including methotrexate, amiodarone, oral steroids or SERMs (such as tamoxifen). The subject will be able to continue in the study if they initiate other medications that are not known to affect liver fat content.

B. Protection Against Risk

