All treatment-related serious adverse events will be reported to the DSMB within 24h of occurrence. In addition, the chair may call ad hoc meetings. The Board will be provided with reports of serious adverse events as they occur and the chair of the committee has the responsibility of calling an ad hoc meeting if the type or frequency of the serious adverse events is of concern. In addition, an ad-hoc meeting may be called to evaluate whether a subject should be unblinded due to safety concerns or a serious adverse event (SAE). If a study subject is unblinded, the PI will not be made aware of the treatment assignment.

The Board may request additional information from the Investigator in the course of its review. The Investigator shall not be present for part of the Board's meeting.

Safety assessments:

3. CBC: at screening, baseline, and 6 months (and hematocrit at 3 months)
4. Pregnancy testing at all visits

The physician investigator will review all laboratory results in a timely manner.

Subjects will be discontinued if they develop:

1. Bleeding event resulting in hospitalization or decrease in hematocrit by >20% from baseline
2. Decrease in hematocrit by >20% from baseline
3. Positive pregnancy test
4. Severe / intolerable side effects of aspirin
5. Development of malignancy
6. Initiation of the following medications: methotrexate, amiodarone, systemic steroids or tamoxifen

Safety Monitoring:

1. Review of all adverse events (expected, unexpected and serious)
Severity, frequency and reporting protocol adherence
2. Review safety assessments described above
3. Review CBC (or hematocrit) results with unblinded monitor
4. Recruitment, enrollment (adherence to eligibility criteria)
5. Dropout rates
6. Protocol changes

Discontinuation Guidelines:

1. Individual:
 - a. Positive pregnancy test
 - b. Severe / intolerable side effects of aspirin
 - c. Bleeding in the gastrointestinal tract
 - d. Decrease in hematocrit by >20% from baseline
 - e. Development of malignancy
 - f. Initiation of the following medications: systemic steroids for >5 days, methotrexate, amiodarone, tamoxifen
2. Study:
 - a. Unexpected severe / frequent adverse events

The major outcome choice following the data review by the Board is: 1) continuing the trial unchanged, or 2) modify the protocol and/or consent form, or 3) terminate the trial.

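### Antithrombotic use bars entry as a bleeding safeguard, but the protocol text supplied has no rule to stop the blinded capsules when such a drug is started during the trial

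*Combined protocol and SAP*

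**What the plan says.** **At entry.** Section III.A, exclusion 10, bars "Current use of other antithrombotics, anticoagulants, or antiplatelet agents"; non-aspirin NSAIDs are expressly outside this bar. Exclusion 9 bars "Aspirin use within the preceding 3 months".

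**The reason given.** Section V.B (Drugs) and the aspirin paragraph of section VI.A (Potential Risks to the Subjects) describe steps taken to reduce aspirin's risks, bleeding among them. One step is to exclude "any subject with current use of any other anti-coagulant or antithrombotic medications".

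**After randomisation.** The medication paragraph at the end of section VI.A says that clinically indicated drugs will not be discouraged. It withdraws subjects who start a drug known to affect liver fat, and then states: "The subject will be able to continue in the study if they initiate other medications that are not known to affect liver fat content".

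**Discontinuation lists.** Section IX (Safety Monitoring) has two. The drug item in the first reads "Initiation of the following medications: methotrexate, amiodarone, systemic steroids or tamoxifen"; in the second, "Initiation of the following medications: systemic steroids for >5 days, methotrexate, amiodarone, tamoxifen". Neither names an antithrombotic or aspirin.

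**Monitoring.** The blood count schedule is "CBC: at screening, baseline, and 6 months (and hematocrit at 3 months"). At the 3-month visit, "Study subjects will be assessed for interim medical history, and any side effects to study drug". Calls ask about compliance, concerns and side effects. Section IX also provides for review of blood counts with an unblinded monitor, an ad hoc DSMB meeting on whether to unblind a subject for safety, and stops for gastrointestinal bleeding, bleeding that leads to hospitalisation, or a hematocrit fall above 20%.

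**The concern.** The protocol treats anticoagulant or antithrombotic use together with study aspirin as a bleeding hazard to be avoided at entry. It also has a rule for new drugs during the trial, stated in three places, so the authors expected such starts. That rule protects the liver-fat endpoint and leaves out the drug class that the protocol itself names as a bleeding risk.

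Suppose a participant develops a clot or an arrhythmia and is put on an anticoagulant as an outpatient. Staff who consult the medication paragraph find that the person may remain in the study and find nothing about the capsules. They have no rule to apply, and the capsules may be aspirin. What is at stake is avoidable bleeding risk in a small number of people.

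Regular clinically prescribed aspirin raises a related but separate issue. It duplicates exposure in the aspirin arm and dilutes the contrast in the placebo arm. The liver-fat rule does not clearly catch it, because section I.A calls aspirin's effect on liver fat in established NAFLD unknown.

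**Working it through.** **1. Entry rule against on-study rule**

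| Drug started or in use | At entry | After randomisation |
|---|---|---|
| Anticoagulant, antiplatelet, other antithrombotic | Barred (exclusion 10); the anticoagulant/antithrombotic bar is listed as a bleeding safeguard | Not named; subject may stay in the study; capsules not mentioned |
| Aspirin outside the study | Barred if used in the prior 3 months (exclusion 9); no bleeding reason stated | Not named; capsules not mentioned |
| Methotrexate, amiodarone, steroids, tamoxifen | Not listed in III.A | Discontinued |

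**2. Would an existing protection respond to the start of the drug?**

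- Interim history at months 3 and 6, calls, on-call physician: may reveal the start; no capsule instruction follows.
- Month-3 hematocrit and unblinded review of blood counts: respond to a laboratory change. Only one scheduled hematocrit falls between baseline and month 6.
- Stops for bleeding or a hematocrit fall above 20%: act after harm.
- Stop for severe or intolerable side effects: does not cover a symptom-free participant who has just started a drug.
- DSMB unblinding route: available for safety concerns, but not tied to a new drug.
- Change log, versions 4 to 10: no entry describes adding such a rule.

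**3. Scheduled contacts between baseline and month 6**

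Section V.A, item 3, lists calls for months 2, 4 and 5. Twice monthly, that is 2 x 3 + 1 visit = 7 contacts; at the once-monthly frequency in the change log, 1 x 3 + 1 = 4. Sections V.B and VI.A promise twice-monthly calls without naming months. If month 1 is included, the counts are 2 x 4 + 1 = 9, or 1 x 4 + 1 = 5. A question about new drugs therefore has 4 to 9 existing contacts to use.

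**4. How often might this happen?**

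The documents give no start rate p. Assume 0.5% to 2% over six months, and 1:1 allocation (the ratio is not stated), so about 40 on aspirin. Expected starts = n x p; chance of at least one = 1 - (1 - p)^n.

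| p (assumed) | Expected, n = 40 | At least one, n = 40 | Expected, n = 80 | At least one, n = 80 |
|---|---|---|---|---|
| 0.5% | 0.2 | 18.2% | 0.4 | 33.0% |
| 1% | 0.4 | 33.1% | 0.8 | 55.2% |
| 2% | 0.8 | 55.4% | 1.6 | 80.1% |

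These are chances of a drug being started. They are not chances of a bleed.

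**5. What would the fix cost in power?**

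Inputs from section VI.C: difference 3, SD of change 2.45, two-sided alpha 0.05, effective sample 80 x (1 - 0.15) = 68, hence 34 per arm at 1:1.

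The plan's figure first: noncentrality = (3/2.45) x sqrt(34/2) = 5.05 with 66 degrees of freedom, giving power 99.87%. The stated value of more than 90% is met.

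Now suppose a fraction p of the aspirin arm stops capsules and each stopper loses the whole effect. The difference becomes 3 x (1 - p), and the aspirin-arm SD becomes sqrt(2.45^2 + 9p(1 - p)).

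- p = 0.5%: difference 2.985, power 99.86%.
- p = 2%: difference 2.94, power 99.80%.

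**The case against.** The strongest reply is that silence is not permission. A reader might infer that the plan directs blinded aspirin to continue alongside an anticoagulant. The text does not say that: it speaks of staying in the study, not of staying on capsules, and nothing stops a physician from holding them. This stands, and the point is limited to the absence of an instruction.

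A reader might also infer that no instruction exists anywhere. The telephone script and consent form are not in the documents and could carry one, and the change log gives only brief summaries. The absence is shown for the protocol text supplied and no further.

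Three other inferences go too far. Exclusion 9 carries no stated bleeding reason and could be a washout, so the bleeding rationale cannot be extended to it. A month-1 gap in calls depends on one parenthetical list, while other sections promise calls with no month limit. The 18% to 55% for the aspirin arm is neither a bleeding risk nor an estimate: the rate is assumed, and the true one may be below 0.5%, because the entry criteria remove recent infarction, active angina and prior bleeding, and the risk sections add stroke.

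What does not stand is the claim that existing safeguards suffice. Some may detect the start and others act after a bleed, but none says what to do with the capsules once the start is known.

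**Conclusion.** The point holds as a cheap safety improvement. The protocol bars antithrombotics at entry, lists the anticoagulant and antithrombotic part of that bar as a bleeding safeguard, and then applies an on-study medication rule that considers liver fat alone. Comparing the sections establishes this without any assumed number.

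The size is small. At the assumed start rates, fewer than one aspirin-arm participant is expected to be affected. A reader might infer a threat to the trial's power or primary result; the calculation does not support that. The numbers rest on the assumed 0.5% to 2%, on 1:1 allocation, and on the plan's own effect size and SD.

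For clinically prescribed aspirin the case is duplicate exposure and dilution of the contrast, and it should be argued on those grounds.

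**What to change.** Add to the medication paragraph in section VI.A, and to both lists in section IX as an item marked as a stop of study capsules only:

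*If an anticoagulant, antiplatelet or other antithrombotic (including regular clinically prescribed aspirin) is started, study capsules are stopped in either arm and the PI is notified. Unblinding is not routine but remains available through the DSMB route when needed for safety. The subject stays in follow-up, has the month-6 assessments whatever the weeks on drug, and remains in the intention-to-treat analysis.*

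The words on weeks are needed because section V.A, item 4, limits the Early Termination visit to people with at least 11 weeks on study medication; an early stopper could otherwise miss the final scan. Non-aspirin NSAIDs stay allowed, as in exclusion 10.

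Add one question on new use of these drugs, with start date, to each existing call and visit.

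Cost: one statement, one item in each list and one scripted question, with no new visits or tests. A few participants may stop study drug, with the negligible loss of power shown above.

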41. Schoenfeld D. Statistical considerations for pilot studies. *International journal of radiation oncology, biology, physics* 1980;6:371-4.

Changes to Study Protocol After Trial Initiation Date:

- Version 4 (Amendment 2; approval date: 09/10/2019) updated the informed consent process descriptions.
- Version 5 (Amendment 5; approval date 10/02/2019) increased the upper age limit from 65 to 70 years; changed the frequency of follow-up phone calls from twice monthly to once monthly as recommended by the MGB QI team; and updated the funding information.
- Version 6 (Amendment 8; approval date 01/06/2020) updated the format of the SF-36 questionnaire; changed the compensation scheme for subjects, while keeping the total compensation for the overall trial unchanged; included the option of a serum pregnancy test for women of childbearing potential (in addition to urine pregnancy test); and included updated written instructions for stool collection kits, for subjects.
- Version 7 (Amendment 10; approval date 09/30/2020): added an oral microbiome sample to the baseline and month 6 time points; updated the payment distribution scheme for each study visit.
- Version 8 (Amendment 11; approval date 11/12/2020): clarified the exclusion criteria for thrombocytopenia by including the definition of lower platelet count threshold of 100K/uL.
- Version 9 (Amendment 12; approval date 02/19/2021): added an optional pre-treatment and/or post-treatment liver biopsy.
- Version 10 (Amendment 17; approval date 08/05/2022): added institution-wide research announcements as an additional method of potential recruitment.

Changes to Statistical Analysis Plan After Trial Initiation Date: none
